5.2. F1 INTERIM ANALYSIS METHODOLOGY

Outcomes A, B, D

For these binary outcomes, they will be summarised as the number and proportion of children who had the outcome as yes between F0 and F1 by treatment groups and by clinical outcome groups.

The comparison between treatment groups will be made using a GLM approach with Gaussian error distribution (to avert convergence difficulties with low prevalence outcomes), linear link function and a cluster-robust standard error calculation to account for clustering by study site. The RD and 95% CI will be derived, adjusted by the age group at randomisation (1-5 years; 6-10 years) and SPT wheal size (≤10mm; >10mm).

The RR (with 95% CI) comparing treatments will also be estimated using a GLM approach (the "modified Poisson" approach of Zou, employing the Poisson family, a log link function and a cluster-robust standard error calculation to account for clustering by site), adjusted by the age group at randomisation (1-5 years; 6-10 years) and SPT wheal size (≤10mm; >10mm).

The comparison between clinical outcome groups will be made using a binary regression model. The RD, RR and 95% CIs will be derived.

Outcome C, F, G

For these categorical outcomes, they will be summarised as the number and proportion of children who had the outcome in each category by treatment groups and by clinical outcome groups. They will also be summarised as the median, IQR and range by treatment groups and by clinical outcome groups.

Outcomes C, E, F, G, I

For these continuous outcomes, they will be summarised as mean and SD or median and IQR by treatment groups and by clinical outcome groups as specified.

The mean difference between treatment groups will be obtained by using GLM to account for clustering by site, adjusted by the age group at randomisation (1-5 years; 6-10 years) and SPT wheal size (≤10mm; >10mm). The median difference using quantile regression model to adjust for the stratification factors if not normally distributed.

The mean difference between clinical outcome groups will be obtained by using a linear regression model. The median difference using quantile regression model if not normally distributed. For outcome I, linear/quantile regression model will be used for further adjusted for baseline QoL score.

Outcome H

We will also compare the QoL scores between treatment groups using a mixed model applied to the data at 4 timepoints (T0, T1, T3/F0, F1) and account for clustering by study site, with fixed effects for treatment, age group at randomisation and SPT wheal size, and a random effect to allow for repeated measures for each individual.

SIGNATURES PAGE

Signature of Group Leader:

[name]

Date 04 -Jun - 2022

Print Name

[name]

Signature of Principal Investigator:

ale

Date 31-May-2022

Print Name

[name]

Signature of Trial Statistician:

Print Name

[name]

Date 10-May-2022

[name]

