1. OBJECTIVES OF THE INTERIM ANALYSIS F1

- 1. To measure and compare peanut intake and reactions to peanut (accidental or intentional ingestion) from end-of-treatment (T1 of PPOIT-003 study) to 24 months (F1) post-treatment:
 - in PPOIT vs OIT vs placebo and
 - in subjects with SU vs DWSU vs allergic.
- 2. To compare change from baseline in quality of life (PPOIT-003 study entry) at 24 months (F1) posttreatment:
 - in PPOIT vs OIT vs placebo groups and
 - in subjects with SU vs DWSU vs allergic.

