2. BACKGROUND/INTRODUCTION

2.1. GENERAL STUDY INFORMATION

(refer to protocol version 4 dated 05 Oct 2021)

Study design

This is a multicentre follow-on study. There is no treatment intervention in this study. However, there will be study assessments performed including skin prick test (SPT) and blood tests. Subjects will remain blinded to their PPOIT-003 treatment allocation and will continue with peanut avoidance / ingestion according to the instructions they received at the end of treatment in PPOIT-003 as outlined below:

- Subjects who were classified as SU at T2 in PPOIT-003 (Group 1) were instructed to introduce • peanut into their diet ad libitum without specific instructions on how often or how much peanut to ingest.
- Subjects who were classified as desensitisation without SU at T2 in PPOIT-003 (Group 2) were instructed to ingest 1-2 peanuts each day to maintain desensitisation.
- Subjects who were classified as allergic at T1 in PPOIT-003 (Group 3) were instructed to continue with strict peanut avoidance.

The classification of these clinical outcome groups was determined as follows:

- SU = Subjects who passed both T1 and T2 challenges in PPOIT003
- DWSU = Subjects who were fully desensitised to cumulative 4950mg peanut protein at end • of treatment (passed T1 challenge) but failed the T2 challenge
- = Subjects who failed the T1 challenge irrespective of whether the reaction Allergic ٠ threshold in T1 challenge had increased from Baseline T0 challenge.

These clinical outcome groups are comprised of subjects in PPOIT-003 who received one of the treatment allocations outlined below however study staff and subjects remain blinded to their treatment allocation:

- PPOIT = Probiotic and peanut OIT taken daily for 18 months during PPOIT-003. •
- OIT = Probiotic placebo and peanut OIT taken daily for 18 months during PPOIT-003.
- = Probiotic placebo and OIT placebo taken daily for 18 months during PPOIT-003. Placebo .

All subjects will be monitored for 60 months (from 12 months post treatment -FO- to 72 months post treatment -F5).

The study consists of:

(FORM: SAP template interim analysis/Version 1.1)

Monitoring phase (up to 60 months)

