This occurs after completion of the T3 visit of PPOIT-003, which coincides with the first visit of the follow-on study (F0). All subjects will be followed up for 60 months after T3/F0 (which is up to 6 years post treatment that was received in PPOIT-003). During this time, all subjects will be monitored for information on exposure to peanut/amount of peanut being eaten and allergic reactions via a mobile diary application (app) until the end of study (72 months post treatment (F5)).

A phone call will be administered at the following time points:

• Time point F1 – 12 months after F0 (24 months post-treatment)

A visit for SPT, bloods and stool will be administered at the following time points:

- Time point F2 24 months after F0 (36 months post-treatment)
- Time point F3 36 months after F0 (48 months post-treatment)
- Time point F4 48 months after F0 (60 months post-treatment)
- Time point F5 60 months after F0 (72 months post-treatment)

Note: Where a face-to-face visit is not possible (eg due to COVID-19 restrictions or other unavoidable circumstances), the visit will be conducted by phone and SPT, bloods and stool test will not be performed.

This study is expected to run for 78 months from the start of participant enrolment to the last participant finishing the study. The length of the study (i.e. follow up period) for each participant is 60 months.

The three sites will be: The Royal Children's Hospital Melbourne / Murdoch Children's Research Institute, The Women's and Children's Hospital Adelaide, Perth Children's Hospital. A maximum of 201 participants will be recruited – the study population recruited to PPOIT-003.

Study population

Subjects meeting the eligibility criteria will be recruited at end of PPOIT-003 without unblinding of PPOIT-003 treatment allocation.

Inclusion criteria

Subjects are eligible for the study if they meet all of the following criteria:

- Were randomised and received at least 1 dose of treatment in PPOIT-003
- Participated in the PPOIT-003 randomised trial
- Written informed consent from participants and/or parent/guardian.

Exclusion criteria

Subjects are not eligible for the study if they meet any of the following criteria:

- Are taking probiotic supplements (does not include formula, yoghurts and fermented foods).
- Withdrew from the PPOIT-003 study.
- Have any condition that, in the opinion of the Investigator, precludes participation for reasons of safety.

Sample size

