4. VARIABLES

4.1. OUTCOMES

Table 1 –Outcomes description

	Outcome	Description
А	Peanut ingestion (intentional or accidental)	Binary outcome
	between T1 and F1	
		1=Yes if ingested peanut at least once over
		the 12 months period.
		0=No
В	Reaction to peanut ingestion (intentional or	Binary outcome
	accidental) between T1 and F1	1=Yes if reacted to peanut at least once
		over the 12 months period
		0=No
С	Number of reactions to peanut ingestion	Continuous outcome
	(intentional or accidental) T1 and F1 overall	
	and by severity	and Categorical outcome
		1=1 reaction
		2=2 reactions
		3=3 or more reactions
D	Use of EpiPen to treat reaction to peanut	Binary outcome
	(intentional or accidental) between T1 and F1	1=Yes if used EpiPen to treat reaction to
	(peanut at least once over the 12 months
		period
		0=No
E	Number of times using EpiPen to treat	Continuous outcome
-	reactions to peanut (intentional or accidental)	
	between T1 and F1	
F	Weekly average quantity of peanut protein	Continuous outcome
	ingested (intentional or accidental) between	
	F0 and F1	and Categorical outcome
		1=Never ingested
		2=Minimal amount (less than 1 peanut,
		<250g)
		3=Small amount (1-2 peanuts, 250-599g)
		4=Moderate amount (3-8 peanuts, 600-
		1999g)
		5=Large amount (>2000g)
G	Weekly average frequency of peanut	Continuous outcome
	ingestion (intentional or accidental) between	
	F0 and F1	and Categorical outcome
		1=Nil
		2=Less than once a month
		3=Once a month to <1/week
		4=1-2 times/week
		5=3-5 times/week
		6=>5 times a week
н	Quality of life scores – total, sub-scores	Continuous outcome. From FAQLQ-PF, tot
	(emotional impact, food anxiety, social and	score is calculated as the mean of up to 30
	dietary limitations) and FAIM total score at F1	items (some are age specific), with
		response scale from 0 (minimal impairmer
		in QoL) to 6 (maximal impairment in QoL).

		The mean scores for selected items are used to construct the sub-scores. The FAIM consists of 4 questions, scored on a 7-point scale. The FAIM total score is the mean of all items and ranges from 0 (limited severity perception) to 6 (greatest severity perception).
I	Change in quality of life scores (total, sub- scores, and FAIM) from screening in PPOIT- 003 study to F1	Continuous outcome

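### Outcomes A, B and D have two incompatible counting windows: T1 to F1 (24 months) in the objective and outcome names, 12 months (F0 to F1) in the coding and section 5.2

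*SAP*

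**What the plan says.** Objective 1 (SAP section 1) covers peanut intake and reactions "from end-of-treatment (T1 of PPOIT-003 study) to 24 months (F1) post-treatment", compared by treatment arm and by clinical outcome group.

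Table 1 (section 4.1) names outcomes A to E with the same T1-to-F1 window; the name of outcome B, for example, ends "accidental) between T1 and F1". In the Description column, A, B and D are scored yes if the event happened at least once "over the 12 months period". The intake outcomes F and G are named F0 to F1.

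Section 5.2 then reports A, B and D as "the number and proportion of children who had the outcome as yes between F0 and F1". It gives no window for C, E, F or G.

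Section 2.1 fixes the calendar. Monitoring runs "from 12 months post treatment", which is F0, and F1 is "12 months after F0 (24 months post-treatment"). On the monitoring phase it says: "This occurs after completion of the T3 visit of PPOIT-003, which coincides with the first visit of the follow-on study (F0"). It also defines the clinical groups. SU children passed both the T1 and T2 challenges. DWSU children were fully desensitised at the end "of treatment (passed T1 challenge) but failed the T2 challenge".

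**The concern.** A row of Table 1 that is both T1 to F1 and 12 months long cannot be derived as written, and section 5.2 repeats only the shorter window. Two analysts following the SAP in good faith could report different numbers of children with a reaction, and different RDs and RRs. If the window is left open, it could also be chosen after the data are seen.

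Two further points follow.

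- **Mixed windows under one objective.** Objective 1 asks for intake from T1, but quantity and frequency (F, G) start at F0. Counts of reactions and EpiPen use (C, E) are named from T1.
- **The T2 challenge.** If counting starts at T1, the window appears to include the challenge that decides whether a child is SU or DWSU. The outcomes cover intentional as well as accidental ingestion, and the SAP does not say that supervised challenge doses or reactions are left out. SU v DWSU is one of the pairwise comparisons listed in section 5.1.

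**Working it through.** **1. Length of each window.** Take end of treatment (T1) as month 0, from objective 1. Section 2.1 puts F0/T3 at month 12 and F1 at month 24.

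- T1 to F1 = 24 − 0 = 24 months.
- F0 to F1 = 24 − 12 = 12 months.

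The 12 months in the Table 1 coding is reproduced only by F0 to F1.

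**2. The statements side by side.**

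| Place in the SAP | Outcomes | Window | Length |
|---|---|---|---|
| Section 1, objective 1 | intake and reactions | T1 to F1 | 24 months |
| Table 1, Outcome column | A, B, C, D, E | T1 to F1 | 24 months |
| Table 1, Description column | A, B, D | start not named | 12 months |
| Table 1, Outcome column | F, G | F0 to F1 | 12 months |
| Section 5.2 | A, B, D | F0 to F1 | 12 months |

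Nothing in the SAP says which of these governs.

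**3. Effect on the estimates (illustration).** The SAP gives no expected event rates, so the risks here are assumed. With the same independent risk p in each of the two years, the 24-month risk is 1 − (1 − p)².

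- 5% v 10% over 12 months: RD 5.0 points, RR 2.00. Over 24 months: 1 − 0.95² = 9.75% v 1 − 0.90² = 19.0%; RD 9.25 points, RR 1.95.
- 20% v 40% over 12 months: RD 20 points, RR 2.00. Over 24 months: 1 − 0.80² = 36% v 1 − 0.60² = 64%; RD 28 points, RR 1.78.

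In these examples the RD changes in both cases. The RR hardly moves when events are rare and moves more when they are common.

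**4. Where T2 falls.** The SAP gives no date for T2. By visit order it comes after T1 and before T3/F0, so it lies inside T1 to F1 and outside F0 to F1.

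**5. What would follow if challenge events were counted.** This needs three conditions: a T1 start, challenge events entering the outcome, and failing a challenge meaning reacting. Outcome B would then be 1 for every DWSU child, and outcome A would be 1 for every SU and DWSU child. Suppose everyday risk were the same in SU and DWSU, at an assumed value p. The apparent DWSU − SU difference in B would be 1 − p and the ratio 1/p:

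- p = 5%: RD 95 points, RR 20.
- p = 40%: RD 60 points, RR 2.5.

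The T1 challenge, on the boundary of the window, raises the same question for the allergic group, who failed it.

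**The case against.** The strongest reply is that the plan's working intention can be read from its text. The only analysis section that gives a window for A, B and D uses F0 to F1, and the 12-month coding fits nothing else. On that reading the objective and the outcome names are loosely worded, and T2 falls outside the window. F and G are weekly averages, for which a recent 12-month window is defensible. This has force as to which window may have been meant. It does not remove the contradiction: T1 to F1 stands in the objective and in five outcome names, so it is not a single slip.

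A reader might infer that outcome B is 100% in DWSU by definition, so that SU v DWSU is circular as planned. The document does not support this. It holds only under the conditions in step 5 of the working. The data sources described are a diary app used after F0 (section 2.1) and a questionnaire at F1 (section 4.2), and neither is said to capture challenge doses. T2 is placed by visit order alone, and section 5.1 loosely labels it end of treatment. Challenge handling may also be settled in the protocol, which is not at hand. What remains is an unguarded risk under a T1 start.

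Two other inferences go too far. The SAP does not rank A, B or D as primary outcomes. It also plans no analysis relating intake to reactions, so the mixed windows in Table 1 are an inconsistency with objective 1 and do not spoil a planned analysis.

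**Conclusion.** The contradiction stands in the current text: 24 months in objective 1 and the outcome names, 12 months in the coding and in section 5.2. It directly affects A, B and D. C and E carry the T1 label with no window in section 5.2, and F and G do not cover the intake period that objective 1 asks for.

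The factor of two in window length follows from the SAP's own timeline. The size of the effect on results is not known from the document. The figures in step 3 rest on assumed risks that are constant from year to year.

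The T2 problem is conditional. It arises only under a T1 start with challenge events counted, and an F0 start avoids it. Even with challenge events excluded, a T1 start would count events between T1 and T2, before SU and DWSU are told apart. The clinical-group comparisons therefore need their own safeguard if T1 is chosen.

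**What to change.** Before unblinding, amend the SAP as follows.

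1. State one window for each of outcomes A to G, with its correct length, identically in objective 1, Table 1 and section 5.2. Either F0 to F1 labelled 12 months, or T1 to F1 labelled 24 months if events between T1 and F0 were recorded in a comparable way. The choice is the sponsor's.
2. State that ingestions and reactions at supervised food challenges do not count in A to E.
3. For the SU, DWSU and allergic comparisons, count only events after T2, or use F0 to F1, so that group membership precedes the outcome.

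The cost is SAP wording and a date filter in the derivation of the outcomes. A T1-to-F1 window also depends on T1-F0 data being available from PPOIT-003. The SAP does not establish this, because the diary monitoring it describes begins at F0.

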No formal sample size calculation is being conducted for the follow-up study. A maximum of two hundred and one (201) participants will be recruited from PPOIT-003 trial (PPOIT n=79; OIT n=83; placebo n=39).

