For continuous outcomes, the mean difference between treatment groups will be obtained by using GLM to account for clustering by site, adjusted by the age group at randomisation (1-5 years; 6-10 years) and SPT wheal size (\leq 10mm; >10mm). The median difference using quantile regression model to adjust for the stratification factors if not normally distributed.

We will also compare the QoL scores using a mixed model applied to the data at 4 timepoints (T0, T1, T3/F0, F1) and account for clustering by study site, with fixed effects for treatment, age group at randomisation and SPT wheal size, and a random effect to allow for repeated measures for each individual.

ESTIMATION OF EFFECTS (BETWEEN CLINICAL OUTCOME GROUPS)

For binary outcomes, a binary regression model will be used.

For continuous outcomes, the mean difference between the clinical outcome groups will be obtained by using linear regression. Adjusted linear regression will be used to adjust for baseline QoL score in outcome I. The median difference using quantile regression model if not normally distributed.

HANDLING OF MISSING DATA

It is anticipated that 25% of children will not continue to participate the follow-up, due to participant attrition and parent/guardian non-response. The available case analysis will be the

(FORM: SAP template interim analysis/Version 1.1)

primary one. A sensitivity analysis using Inverse Probability Weighting (IPW) and Multiple Imputation (MI) techniques will be used to handle the missing data (details in section below).

SENSITIVITY ANALYSIS

The sensitivity analysis will be performed on an intention-to-treat basis including all the children whose parent/guardian consented for follow-up, with IPW and MI techniques used to handle the missing data. It is anticipated that 25% of the original sample of 201 children will have follow-up outcomes missing. In such situations, we will use both MI combined with IPW techniques (Seaman, S.R., White, I.R., Copas, A.J. and Li, L., 2012. Combining multiple imputation and inverse-probability weighting. Biometrics, 68(1), pp.129-137.) as a sensitivity analysis. It involves two major steps:

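### Risk-difference and relative-risk intervals for outcomes A, B and D rest on standard errors clustered on only three sites, with no small-sample correction; these standard errors are erratic and on average too small

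*SAP*

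**What the plan says.** SAP section 2.1 introduces the list of centres with "The three sites will be" and names three. It gives the maximum sample as "PPOIT n=79; OIT n=83; placebo n=39".

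SAP section 5.2 (Outcomes A, B, D) sets the treatment comparison as follows:

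- Risk difference (RD): a Gaussian GLM with "linear link function and a cluster-robust standard error calculation to account for clustering by study site". The text continues: "The RD and 95% CI will be derived, adjusted by the age group at randomisation" and by skin-prick-test wheal size.
- Relative risk (RR): modified Poisson, "employing the Poisson family, a log link function and a cluster-robust standard error calculation to account for clustering by site", with the same two covariates.

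No t reference, degrees of freedom, finite-sample correction or site covariate is given for either model.

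For continuous outcomes, section 5.1 says only that "the mean difference between treatment groups will be obtained by using GLM to account for clustering by site", without naming a type of standard error. Comparisons between clinical outcome groups use a binary or linear regression with no clustering stated, so they lie outside this point.

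**The concern.** A sandwich variance clustered on site estimates variability from the differences between site-level score totals, and its justification needs many clusters. Here it has three, which leaves about two degrees of freedom however many children are followed. The estimate is then biased downward on average and varies greatly from one data set to the next. If it is combined with 1.96, intervals labelled 95% do not cover 95% of the time.

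These are the only inferential results planned for the treatment comparisons of ingestion, reaction and EpiPen use, which carry the first objective in SAP section 1. A reader of the F1 report could take chance differences between PPOIT, OIT and placebo as established, or see an interval whose width is largely an accident of how the three sites fell.

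**Working it through.** The SAP has no coverage or power figure to reproduce. The arm sizes do add up: 79 + 83 + 39 = 201.

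**Inputs from the SAP.** Three sites; individual randomisation; models with two treatment terms, age group and wheal size; nominal level 95%. On attrition: "It is anticipated that 25% of the original sample of 201 children will have follow-up outcomes missing". Retained numbers: 0.75 × 79 ≈ 59, 0.75 × 83 ≈ 62, 0.75 × 39 ≈ 29, about 150 in total.

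**Assumptions (not in the SAP).** Site shares 33/33/33, 60/20/20 and 80/10/10; event risk 5% to 60%; between-site SD of risk 0 to 0.08; no treatment effect; finite-sample factor G/(G−1) = 3/2 applied to the clustered variance.

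**Closed form for three equal sites.** The clustered statistic behaves roughly as t with 2 degrees of freedom, for which P(|t| < c) = c / √(2 + c²).

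- c = 1.96: 1.96 / √(2 + 3.84) = 1.96 / 2.417 = 0.81.
- c = 4.303: 4.303 / √(2 + 18.52) = 4.303 / 4.529 = 0.95, at 4.303 / 1.96 = 2.2 times the width.

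**Simulation of the RD interval** (typically 2,500 to 4,000 data sets per scenario; ranges run over event risk, between-site SD and the three pairwise comparisons):

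| Assumed site split | Coverage, z = 1.96 | Coverage, t on 2 df | Median ratio, clustered SE to participant-level robust SE | Data sets where clustered SE is the larger |
|---|---|---|---|---|
| 33/33/33 | 79–85% | 93–97% | 0.82 | about 35% |
| 60/20/20 | 75–80% | 93–97% | 0.75 | about 29% |
| 80/10/10 | 56–70% | 86–91% | 0.57 | about 14% |

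The 10th to 90th percentile range of that ratio is about 0.3–1.5, 0.3–1.4 and 0.2–1.1 for the three splits.

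**One scenario in full.** 60/20/20, risk 30%, between-site SD 0.08: coverage is 70–71% without the G/(G−1) factor, 77–78% with it, 94% with t on 2 df, and 94–95% with participant-level robust standard errors. For the first of the three comparisons, the mean clustered SE is 0.0818 against a true sampling SD of 0.105, a ratio of 0.78.

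**More children do not help.** With no attrition (79/83/39), 60/20/20 and 30% risk, coverage with z is still 77–78%.

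**RR interval** (equal and 60/20/20 splits only): 76–82% with z, 93–96% with t on 2 df, 95–98% with participant-level robust standard errors.

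**Participant-level robust standard errors for the RD:** about 93–96%, with or without site indicators. At a 5% event risk, HC3 with site indicators gave 92–93%.

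**The case against.** **The critical value is not stated.** The SAP does not commit to 1.96. If the analyst used t on 2 df, coverage would be close to nominal unless the sites are very unequal. This stands as a limit on the size of the shortfall, but it does not rescue the plan: the correction is not written down, the intervals become 2.2 times wider for a given standard error, and the standard error stays erratic.

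**Not every interval is too narrow.** A reader might infer that all treatment comparisons will have intervals far too narrow. The results do not support that. In roughly 14–35% of data sets, depending on the split, the clustered standard error was the larger one. The defect is instability with a downward bias on average.

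**Rank.** The three site score vectors sum to zero, so the clustered variance has rank 2 for a five-parameter model. That would block a joint test of more than two terms, but section 5.1 plans only pairwise contrasts, so nothing turns on it.

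**Other outcomes.** A reader might extend the point to the continuous outcomes and the quality-of-life mixed model. For the former, the wording also fits a site term, so it is ambiguous and not shown to be wrong. For the latter, the SAP specifies a mixed model, not a sandwich variance, and nothing here shows that it fails.

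**No decision rule.** The SAP sets no alpha or success criterion for this interim report, so no trial decision hangs on these intervals. That is fair, but they are still to be reported as 95% intervals.

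**Site indicators can fail in a log-link model.** With 80/10/10 and 150 children, a small site has 15. At 10% risk it has no events with probability 0.9^15 = 21%, and at least one of the two small sites has none with probability 1 − 0.79² ≈ 37%. This stands, and the fix allows for it.

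**Conclusion.** The point holds for the RD and RR treatment comparisons of outcomes A, B and D. As specified, the standard error cannot be relied on with three sites. With normal critical values the non-coverage is about 15–21% with equal sites, 20–25% with 60/20/20 and 30–44% with 80/10/10, instead of 5%. With t on 2 df it is about 3–7% for the first two splits and 9–14% for the third.

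These figures depend on the assumed site splits, event risks and between-site variation, and on a critical value that the SAP leaves open. They should not be read as the trial's actual type I error. With z = 1.96, under-coverage appeared in every scenario tried. For the continuous outcomes the finding is only that the text needs to be made definite.

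**What to change.** In SAP section 5.2, for the RD and RR models of outcomes A, B and D, replace the site-clustered standard error with participant-level heteroscedasticity-robust standard errors (for example HC3). Add site as a fixed effect (two indicators) where event counts allow, and state in advance that site is left out of the log-link model if a site has no events. Because children were randomised individually, the treatment contrast does not need clustering by site to be valid.

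For the continuous outcomes in sections 5.1 and 5.2, state what accounting for clustering by site means. If a site-clustered standard error was intended, use the same participant-level approach. No change to the quality-of-life mixed model is called for on this ground.

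Cost: one sentence in the SAP and one option in the code. Up to two more parameters are fitted. Intervals will usually, though not always, be wider than under the present plan, and for very rare events (about 5% risk) coverage may still fall slightly short, at 92–93%.

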5. STATISTICAL METHODOLOGY

5.1. F1 GENERAL METHODOLOGY

Outcomes will be analysed by treatment group, according to the group to which subjects were originally randomly allocated, regardless of subjects' compliance to treatment during the PPOIT-003 study, or crossover to other treatments. The following pairwise comparisons will be of interest:

- PPOIT vs Placebo
- PPOIT vs OIT
- OIT vs Placebo

Outcomes will also be described by the clinical outcome achieved at end of treatment in PPOIT-003 (T2 PPOIT-003), that is SU, DWSU without SU and Allergic. The following pairwise comparisons will be of interest:

(FORM: SAP template interim analysis/Version 1.1)

- SU vs DWSU
- SU vs Allergic
- DWSU vs Allergic

All demographic and continuous outcomes (collected at T0 and T3/F0) will be presented as mean and standard deviation (or medians and interquartile ranges for skewed data), whilst categorical outcomes will be presented as absolute and relative frequencies in the three treatment groups and clinical groups. Table of characteristics at T0 will be presented by treatment groups for those consented to roll over to PPOIT-003LT; Table of characteristics at T3/F0 will be presented both by treatment groups and by clinical outcome groups.

In this interim analysis, subjects who are withdrawn at the end of the PPOIT003 study will not be included in any analyses. All the outcomes will be reported in available cases who consented to roll over to PPOIT-003LT.

MEASURES OF TREATMENT EFFECT

Risk difference (RD) and relative risks (RR) between treatment groups (or clinical outcome groups) will be the measures of treatment effect for binary outcomes. Mean difference between treatment groups (or clinical outcome groups) will be the measure of treatment effect for continuous outcomes whose distribution is reasonably symmetrical. Median difference between treatment groups (or clinical outcome groups) will be the measure of treatment effect for continuous outcomes whose distribution is severely skewed.

ESTIMATION OF TREATMENT EFFECTS (BETWEEN TREATMENT GROUPS)

For binary outcomes, a generalized linear model (GLM) approach will be used and account for clustering by site, adjusted by the age group at randomisation (1-5 years; 6-10 years) and SPT wheal size (\leq 10mm; >10mm).

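### SU, DWSU and Allergic are non-randomised groups, yet their comparisons carry no age or SPT adjustment and are labelled as treatment effects

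*SAP*

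**What the plan says.** Section 2.1 defines the clinical outcome groups by the PPOIT-003 food challenges. SU, for example, is "Subjects who passed both T1 and T2 challenges in PPOIT003"; DWSU passed T1 and failed T2, and Allergic failed T1. The same section records that the three groups were given different instructions about eating peanut.

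For the binary outcomes, section 5.1 says "For binary outcomes, a binary regression model will be used" between clinical groups. Section 5.2 repeats this for A, B and D ("The comparison between clinical outcome groups will be made using a binary regression model") and adds "The RD, RR and 95% CIs will be derived". Family, link, variance estimator and covariates are not named. For the continuous outcomes, "The mean difference between clinical outcome groups will be obtained by using a linear regression model", or quantile regression if the data are not normal. The only covariate given for any clinical-group comparison is baseline quality of life, for outcome I.

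The randomised arms are treated differently. Their models are adjusted for age group at randomisation and SPT wheal size and account for site. Their risk difference comes from a Gaussian model, chosen "to avert convergence difficulties with low prevalence outcomes".

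On labelling, section 5.1 first says "Outcomes will also be described by the clinical outcome achieved at end of treatment in PPOIT-003", then lists three pairwise comparisons, and then states: "Risk difference (RD) and relative risks (RR) between treatment groups (or clinical outcome groups) will be the measures of treatment effect for binary outcomes". Mean and median differences are given the same label.

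**The concern.** SU, DWSU and Allergic form after randomisation, so nothing in the design balances them on age, sensitisation or site. The comparison most open to confounding is the one left without age or SPT, while the comparison protected by randomisation has both.

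Both objectives in section 1 rest in part on these contrasts. If children in one clinical group were younger or less sensitised at entry, part of any difference in peanut intake, reactions or quality of life would come from that. The treatment-effect label invites readers to credit all of it to the clinical outcome.

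A smaller matter follows for A, B and D. The SAP expects low prevalence and guards against it for the arms. For the clinical groups it promises a risk difference, a relative risk and intervals without saying what happens when a group has no events.

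**Working it through.** **Figure to reproduce.** There is none. Section 2.1 gives the arm sizes, 79 + 83 + 39 = 201, and section 5.1 expects 25% missing: 201 × 0.75 = 150.75, about 151 children. The sizes of SU, DWSU and Allergic, their event rates and their covariate balance are not stated. Every input in steps 2 to 4 is therefore an assumption.

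**Step 1. Covariates named in sections 5.1 and 5.2.**
- Arms, A to G and I: age group and SPT wheal size, with site accounted for (quantile regression: stratification factors only).
- Clinical groups, A, B, D: none.
- Clinical groups, C, E, F, G: none.
- Clinical groups, I: baseline quality of life only.
- T0 characteristics: tabulated by arm only. T3/F0 characteristics: by arm and by clinical group.

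The T3/F0 table is post-treatment, so its SPT values do not show how the clinical groups differed at entry.

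**Step 2. Size of confounding.** For one binary covariate, bias in the unadjusted risk difference = (difference in covariate prevalence between groups) × (risk difference due to the covariate).
- Low end: 0.20 × 0.10 = 0.02.
- High end: 0.40 × 0.30 = 0.12.

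That is 2 to 12 percentage points.

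**Step 3. Chance that a group has no events.** Probability = (1 − p)^n.
- n = 30: 55% at p = 2%, 21% at 5%.
- n = 40: 0.98^40 = 45%; 0.95^40 = 13%.
- n = 50: 36% at 2%, 8% at 5%.

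An empty group is plausible for a rare outcome such as EpiPen use (D).

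**Step 4. What an empty group does to the estimates.** Groups of 60, 30 and 60 were assumed, with no covariates.

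Events 0, 3 and 5, with the empty group as reference:
- Binomial-identity: risk differences 0.100 (SE 0.055) and 0.083 (SE 0.036).
- Gaussian-identity with robust errors: the same estimates and SEs.
- Binomial-log: log relative risks 22.1 and 21.9, each with SE about 15,459.
- Modified Poisson: log relative risks about 22, SE not computable.

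Events 2, 0 and 5, with the empty group as a comparator: modified Poisson gave a log relative risk of −20.4 with SE 0.72. This looks precise but means nothing. Binomial-log gave SE about 13,261.

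Events 60, 28 and 10, so one group is full: risk differences and relative risks were finite under all four models.

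So without covariates the risk difference survives an empty group and only the relative risk is lost. The risk difference's SE needs care, because the empty group contributes no variance: √(0.0833 × 0.9167 / 60) = 0.036 comes wholly from the group with 5 events.

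**Step 5. After covariates are added.** The model is no longer saturated. A binomial-identity fit must keep every fitted risk between 0 and 1 and may not converge at low prevalence. The Gaussian-identity fit has no such constraint, which is the reason the SAP itself gives for using it for the arms.

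**The case against.** The best defence is that the contrasts are meant to be descriptive. Section 5.1 introduces them as description, and its estimation heading for the clinical groups speaks of effects, not treatment effects. A family asking what happens to SU children compared with allergic children is asking a prognostic question, and the unadjusted contrast answers it. Adjustment also cannot remove the different peanut instructions, which bear directly on ingestion and reactions. The age-subgroup analysis covers all outcomes and is not restricted to the arms, so age is partly examined already.

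Much of this stands, and it is why the unadjusted figures should stay. It does not excuse the sentence that labels these contrasts as treatment effects, and it does not let a reader see how far age and sensitisation explain them. The age subgroups leave SPT untouched and split already small groups.

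Three stronger readings are tempting and are not supported:
- A reader might infer that binary regression breaks down altogether with empty or full groups. The SAP names no link, and steps 4 and 5 show that, without covariates, only the relative risk with an empty group is lost.
- A reader might infer that copying the arms' modified Poisson model would cure this. It would not.
- A reader might ask for PPOIT-003 allocation as a required covariate. Allocation is a cause of group membership, so adjusting for it changes the question, and it may be unstable if it strongly predicts the group.

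**Conclusion.** The point holds as a matter of adjustment, labelling and incomplete specification. The SAP compares groups defined by post-randomisation challenge results with no covariates for A to G and only baseline quality of life for I, and it calls the contrasts measures of treatment effect. That much is in the text and needs no assumption.

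The size is not known. The 2 to 12 points and the 13% to 45% chance of no events illustrate assumed imbalances, covariate effects, group sizes and event rates. The SAP does not show that the groups do differ in age, SPT or site. It only gives no protection, and no T0 table, if they do. The lack of a zero-event rule affects the relative risk for rare binary outcomes, chiefly D.

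**What to change.** In sections 5.1 and 5.2:

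1. Keep the unadjusted clinical-group figures. Beside them, for every outcome compared between clinical groups, add a model adjusted for age group at randomisation and PPOIT-003 baseline SPT wheal size, with site as a further covariate where numbers allow. Keep baseline quality of life for outcome I.
2. Present T0 characteristics by clinical outcome group as well as by arm.
3. Remove the treatment-effect label from these contrasts and call them associations. State that the groups also received different peanut instructions, which adjustment cannot remove.
4. For the adjusted risk difference in A, B and D, name the Gaussian-identity model with participant-level robust errors.
5. Where a group has no events, report the counts and the risk difference with an exact or score-type interval, and give no model-based relative risk.

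The covariates are already collected, so the cost is SAP wording and one more table. The downside is a few more parameters in small groups, which is why site is conditional and the unadjusted figures stay.
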